Research hypothesis: Patients who are seen during a virtual phone visit will report different PRO and patient satisfaction scores compared to patients who are seen during an in-person visit for post-operative follow-up at 6 weeks, 12 weeks, and 6-months.

5) Background

Since the WHO declared the coronavirus disease 2019 (COVID-19) a global pandemic on March 11, 2020, health systems have had to reorganize and change the way healthcare is provided to patients [1]. An emphasis has been placed on social distancing to limit the spread of the severe acute respiratory syndrome coronavirus 2 (SARS-CoV-2). In the past several months, healthcare has rapidly shifted towards telemedicine to limit the COVID-19 spread. Telemedicine is defined as healthcare where clinicians utilize technology and telecommunications to treat and diagnose patients [2]. Benefits of telemedicine has been found to include decrease healthcare costs, decrease overall appointment times, and similar patient satisfaction [3-4]. During the age of COVID-19, telemedicine has played a vital role in allowing the conservation of resources like personal protective equipment (PPE), decrease in risk of clinician exposure to COVID-19, and maintain social distancing.

Telemedicine has been researched in various medical specialties and have been associated with good outcomes and patient satisfaction scores [5]. Based on the literature, the use of telemedicine in orthopedics has not been extensively studied. There are studies on virtual fracture clinics which have grown in use in the United Kingdom and Ireland, however, they do not utilize a live assessment model [6-8]. One study looks at patient satisfaction of those seen at a regional medical center in rural Norway through telemedicine [9]. Also, there are studies exploring the use of telemedicine to provide follow-up care after

Patient reported outcomes from patients seen in virtual phone visits compared to in-person physical visits for post-operative follow-up at a sports medicine clinic: a prospective randomized controlled trial

total hip and knee arthroplasty [10-13] and the role of telemedicine by physical therapists as a viable option for virtual rehabilitation [14]

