Researchers want to allow patients to have enough time to read the information sheet and consider participation in this study.

In-person consent will be done at any in-person visit including the pre-operative appointment, day of surgery, and at the routine 2-week postop visit.

How: The Participant will be recruited in-person.

Source of the Participants: Patients that present to the Harbor-UCLA Medical Center sports medicine clinic that have scheduled operative intervention.

Methods to identify potential Participants: When patients of the sports medicine clinic have planned operative intervention, study team member will go through the patient charts to see if patient meets criteria and then discuss and consent the Participant in-person.

Materials to recruit Participants: Patients who meet criteria will be given the information study sheet to review on their own.

Patient reported outcomes from patients seen in virtual phone visits compared to in-person physical visits for post-operative follow-up at a sports medicine clinic: a prospective randomized controlled trial

There are no payments to any of the Participants.

b) Inclusion and Exclusion Criteria

Inclusion criteria:

Participants are at least 18 years of age. Participants who are seen at Harbor-UCLA Medical Center sports medicine clinic. Participants have agreed to have operative intervention. Participants must own a phone with reliable calling capabilities. The Participants must have access to reliable internet to fill out the online survey. The Participants must be able to provide consent. Participants may include pregnant patients. Participants who start out in the virtual phone pathway, and the clinician deems person to require an in-person appointment at the 2-week follow-up visit can be moved to the in-person pathway.

Exclusion criteria:

Patients that are under the age of 18, any cognitive impaired adult, and any adult unable to provide consent.

c) Local Number of Participants

For a statistical significance of 0.05, Power of 80%, and assuming a medium effect size of 0.8, 26 patients are required per group for a total of 52 Participants.

The number of Participants need to complete the research procedure are 52.

Locally we will attempt to recruit at least 104 Participants. This will allow room in case of patients are removed or fall from the study.

d) Study-Wide Number of Participants

This is not a multicenter study.

e) Study Timelines

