The Participant will be notified at the 2-week post-op or after if they will receive in-person follow up or virtual phone follow-up. If the Participant in the virtual phone group feel they need an in-person visit, the Participant will be free to make an in-person follow-up. After each follow up visit (6-week, 12-week, and 6-month), the Participant will be asked to fill out 30-minute surveys.

The surveys the Participant will be asked to fill out are the following:

1. KOOS- a knee specific survey
2. Quick Dash Outcome Measure
3. PROMIS Global
4. General Health Questionnaires (2)
5. Patient Satisfaction Survey -We will have the patient complete this also after every visit to see if their preferences change over time as their recovery changes.

If a Participant attends an in-person post-operative follow up visit, then the study team member will check to see if the participant is on the in-person list. If the participant is on the list, then he or she will be given a tablet to fill out the online survey after the appointment. The tablet will be set up so a link to the surveys can be accessed and participants can fill out the surveys. The surveys are on REDCaps (<https://research.lundquist.org/redcap/surveys/?s=NK3YH4NWL3>). Patients will be able to fill out the survey at home. For Participants that attend a virtual appointment, an online

Patient reported outcomes from patients seen in virtual phone visits compared to in-person physical visits for post-operative follow-up at a sports medicine clinic: a prospective randomized controlled trial

link to the survey on REDCap will be sent to the Participant's email. Members of the study team can also call the participant to conduct the survey over the phone. The emails will be made secure by having them sent out from an official DHS email that uses Microsoft outlook and requires double verification to logon. The content of the email message is included in the IRB submission as a separate document.

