The first page of the survey asks for the Participant's name, date of birth, and preferred language (English or Spanish), how comfortable filling out the form, who is completing the form, which joints, amount of pain, and amount of back pain. The second page of the survey will be a joint specific survey and will depend on the joint selected on the first page and the language chosen. It can be the KOOS, QuickDash Outcome Measure, or PROMIS Global. There is a separate patient satisfaction survey that the patient will complete.

Participants will have appointments with the surgeon for suture removal (10 to 14 days after surgery), and evaluation at 6 weeks, 12 weeks, and 6 months after surgery per usual practice.

The source records that will be used to collect data about the Participants are the surveys, and type of surgery, and results of follow up visits. The data collected will be asked on the surveys which include demographic information- Participants' injury region, age, gender, and time since operative intervention.

Study coordinator will check the upcoming Participant schedule and ensure the correct appointment is scheduled.

h) Data and Specimen Banking

None. No data or specimen banking will be done.

i) Data Management/Statistical Analysis

Statistical analysis will be conducted to compare the total scores of each survey results from participants in the in-person group with participants in the virtual phone group. Each Participant outcomes scores will be averaged with standard deviation calculated.

Participant outcomes scores from each appointment time frame (6-week, 12 week, and 6 months) will be compared across the in-patient group and virtual phone group using Student t-test. Statistical significance will be based on an α level of 0.05.

To determine if there is a difference among the Participants' preference for an in-person visit or telemedicine visit, we will conduct a chi-squared test comparing the percentage of Participant responses from the in-patient group with responses from virtual phone group.

Within each category, to determine if Participant's satisfaction changed as time progressed, we will conduct an Analysis of Variance. This will help us determine

Patient reported outcomes from patients seen in virtual phone visits compared to in-person physical visits for post-operative follow-up at a sports medicine clinic: a prospective randomized controlled trial

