if Participants who experience virtual phone visits start to have changing satisfaction the longer time has elapsed since initial operative intervention.

The PROMIS Global is used to calculate the required sample size as it is the largest range of the outcome measures resulting in the most conservative estimates.

For a statistical significance of 0.05, Power of 80%, and assuming a large effect size of 0.8, 26 Participants are required per group for a total of 52 Participants.

At the end, study data will be exported into excel sheets. All the data collected will be on an excel spreadsheet for purposes of the study. Individual surveys will not be downloaded. At that time, all identifiers will be removed and a de-identified data set is maintained and analyzed. At this time, the study team will not be able to identify which data belongs to which participant. Once this occurs, a subject will not be able to request removal of their data. This spreadsheet will be stored on the secure One Drive Microsoft account which uses double authentication and is provided to all DHS employees. Data originating from the surveys will also be kept in a password-protected location on the Harbor-UCLA One Drive Microsoft account. Data will be stored for 3 years after study completion. Access to the data will be given only to those registered with the study.

Signed consent documents any other paper records are kept in a locked cabinet in a locked office with limited access. The data will be stored for 3 years after completion of the research project.

The only individuals with access to the information will be members of the study team.

j) Confidentiality

A list of Participants participating in the study will include the Participant's name, element of dates, which experiment group the Participant is a part of, MRN, and phone number and email, and study ID number. No health information is recorded with this list. This list is kept on the Harbor-UCLA One Drive Microsoft account and available to the research team. All health data required will be recorded in REDCap hosted by Lundquist and the data will include direct identifiers such as name.

k) Provisions to Monitor the Data to Ensure the Safety of Participants

This research does not result in more than minimal risk to the Participants.

l) Withdrawal of Participants

Participants can withdraw from the study at any time.

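### With no pre-allocation patient-reported score and an unadjusted t-test that ignores covariates already collected, the plan loses precision and leaves chance imbalance uncorrected

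*Combined protocol and SAP*

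**What the plan says.** - **Timing of scores (section 9g).** "After each follow up visit (6-week, 12-week, and 6-month), the Participant will be asked to fill out 30-minute surveys". No section schedules PROMIS Global, KOOS or QuickDASH at the pre-operative visit, on the day of surgery or at the 2-week visit.
- **Analysis (section 9i).** Scores at each time point "will be compared across the in-patient group and virtual phone group using Student t-test" (the in-patient group is evidently the in-person arm). No covariate is named. The ANOVA in the same section looks at satisfaction over time within a group and does not adjust the arm comparison.
- **Covariates available (section 9g).** The surveys record "injury region, age, gender, and time since operative intervention", and type of surgery comes from the source records.
- **Allocation (section 9g).** Block randomisation after consent, with no stratification factor named.
- **Size (sections 9c and 9i).** "For a statistical significance of 0.05, Power of 80%, and assuming a large effect size of 0.8, 26 Participants are required per group". Section 9c gives 52 as the number who must complete and at least 104 as the recruitment target.

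**The concern.** The primary endpoint, PROMIS Global, is to be compared across patients with different injured joints and different operations. Such patients probably differ in health before visit mode can have any influence. With 26 per arm and no stratification, the arms can differ by chance in starting health or in joint mix, and an unadjusted comparison carries part of that difference into the estimated effect of visit mode.

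A score taken before allocation would remove the outcome variance it explains and would show how alike the arms were. It cannot be reconstructed once participants have moved into their follow-up arms. The covariates already collected could do part of the same work, but the plan gives them no role in the arm comparison.

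**Working it through.** **Inputs.** From the documents: α ("Statistical significance will be based on an α level of 0.05"), 80% power, d = 0.8, 26 per arm, and 104 recruited (52 per arm if all are analysed). Sidedness is not stated; the hypothesis that virtual-visit patients "will report different PRO and patient satisfaction scores compared to patients who are seen during an in-person visit" implies two-sided. No SD is given, so everything is in SD units. Assumed, because the documents give neither: the correlation r between baseline score and outcome, and the share R² of outcome variance explained by injury region.

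**1. The plan's own figure.** Two-sample t-test, noncentral t, two-sided: n = 25.5, rounded up to 26 per arm, as stated. A one-sided test would need 21. Power at 26 per arm is 80.7%.

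**2. Adding a baseline score.** ANCOVA reduces the residual SD by the factor √(1 − r²), so the effective effect is d/√(1 − r²). One degree of freedom is lost (2 × 26 − 3 = 49). The formula ignores the slight cost of estimating the slope.

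| r (assumed) | effective d | power at 26 per arm |
|---|---|---|
| none (t-test) | 0.80 | 80.7% |
| 0.2 | 0.8/√0.96 = 0.82 | 82.3% |
| 0.3 | 0.8/√0.91 = 0.84 | 84.2% |
| 0.5 | 0.8/√0.75 = 0.92 | 90.4% |
| 0.7 | 0.8/√0.51 = 1.12 | 97.7% |

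The effect detectable with 80% power falls from 0.79 SD to 0.76, 0.69 and 0.57 SD at r = 0.3, 0.5 and 0.7. At r = 0.5, 26 per arm with ANCOVA is worth about 26/0.75 ≈ 35 per arm with the t-test.

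**3. Injury region alone.** Same formula with R² in place of r². R² = 5%, 10%, 20% gives power of about 83%, 85% and 88%.

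**4. Chance imbalance at 26 per arm.** The between-arm difference in a baseline score has SE √(2/26) = 0.28 SD. It exceeds 0.25 SD in 37% of trials and 0.5 SD in 7%. A 0.5 SD difference moves the unadjusted estimate by 0.5r, that is 0.15 to 0.35 SD for r = 0.3 to 0.7. If half the patients are knee patients (assumed) and allocation is unstratified and treated as independent, the knee share differs between arms by 15 points or more in 33% of trials.

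**5. If all 104 are analysed.** At 52 per arm and d = 0.8, unadjusted power is 98.1%, and 99.7% with r = 0.5. The baseline SE falls to 0.20 SD and the chance of a difference above 0.5 SD to 1%. At a smaller effect the gain remains: for d = 0.5, 71% unadjusted against 83% with r = 0.5. Section 9c in fact labels the assumption differently ("assuming a medium effect size of 0.8, 26 patients are required per group for a total of 52 Participants") from the large effect named in section 9i.

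**The case against.** **The t-test is valid and the design meets its stated power.** This stands. A reader might infer that the estimate is biased or the type I error inflated. Randomisation rules that out: chance imbalance is already allowed for in the 5% level. The argument is about efficiency and about how a particular imbalanced result would be read.

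**Imbalance can be seen and corrected.** This stands for injury region, age, gender and type of surgery. A reader might infer that nothing could detect or correct an imbalance in joint. The data for that are collected, and an adjusted analysis could still be specified before the data are seen. Only the missing baseline score is irrecoverable.

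**This is not a 52-patient trial.** Section 9c aims for at least 104 recruits; 52 is the number of completers required. With most of the 104 analysed, little power is gained at d = 0.8. The 26-per-arm figures describe the minimum the plan accepts.

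**The gain rests on assumed values.** It does. At r = 0.2 it is under 2 points, and nothing in the documents shows how well a score about two weeks after surgery predicts one at 6 months.

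**Region adjustment does not help everywhere.** KOOS is knee-only, so region does nothing there. Section 9g lists PROMIS Global among the surveys for all participants but also describes the second survey page as KOOS, QuickDASH or PROMIS Global according to joint. Whether every joint receives PROMIS Global needs clarifying.

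**A 2-week score may come too late.** Sections 9a and 15 allow consent before surgery, and randomisation follows consent. Section 9b speaks of participants in the virtual pathway being moved at the 2-week visit, so some allocations may be known by then. The survey has to be tied to allocation, not merely to the visit.

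**Conclusion.** The point holds as a matter of precision. The plan takes no score before allocation and uses none of its collected covariates in the arm comparison. At 26 completers per arm and d = 0.8, a baseline score would raise power from 80.7% to between 82% and 98% over assumed r = 0.2 to 0.7. Injury region alone would raise it to about 83-88% over assumed R² = 5-20%. The benefit at d = 0.8 shrinks to a point or two if nearly all 104 are analysed, and is larger if the true effect is smaller.

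The documents do not support a finding of bias, of an invalid test, or of imbalance that nothing could correct. The change is still worth making: part of it costs nothing, and the other part cannot be made later.

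**What to change.** 1. **Analysis.** In section 9i, replace the t-test with a prespecified ANCOVA, or an equivalent mixed model, for PROMIS Global at each time point, adjusting for injury region. This needs no new data.
2. **Baseline score.** Have every participant complete PROMIS Global and the relevant joint form on the clinic tablet before being randomised, or at least before allocation is revealed, at the same time point for all. Randomising at the 2-week visit after the survey would achieve this. Include the score as a covariate.
3. **KOOS.** Adjust for the baseline KOOS score rather than for region.
4. **Limits on covariates.** Do not use the pain items on the first survey page of the follow-up surveys as baseline covariates; they are recorded after allocation.

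The cost is one extra survey at a visit already attended, on tablets the clinic already has. It would be shorter than the full 30-minute packet, though the documents give no time for the subset, and section 10 already lists survey time as a burden.

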The study will be ongoing until the appropriate number of Participants are recruited from this site.

The duration of an individual Participant's participation in the study will be from initial visit where consent is asked until completion and submission of the surveys at their 6-month post-operative appointment.

The duration anticipated to enroll all study Participants will be 6 months.

The estimated date for the investigators to complete this study (complete primary analyses) is December 2023.

f) Study Endpoints

Primary study endpoints: Participant reported outcome scores through PROMIS Global.

Patient reported outcomes from patients seen in virtual phone visits compared to in-person physical visits for post-operative follow-up at a sports medicine clinic: a prospective randomized controlled trial

Secondary study endpoints: Patient survey scores for knee injuries via KOOS, and shoulder and elbow injuries via QuickDash. Patient appointment satisfaction scores will be surveyed.

g) Procedures Involved in the Human Research

There are no procedures performed.

The mentioned above surveys will be attached to this document.

Study Design:

In this prospective study, we will enroll patients undergoing operative intervention at a Sports Medicine clinic.

The patient will arrive at the 2 week post-operative appointment to sign the consent form in the presence of study team member and a witness in order to be eligible to participate in the study.

After consent is obtained, the Participant will be randomized to either in-person follow up or virtual phone follow up to take place after the 2-week post-op visit. The virtual visits will occur using the same platforms that they are currently taking place in accordance and required by LA County DHS/HUMC.

The randomization process will utilize block randomization and be conducted by an online program called <http://www.randomization.com>. (Wichmann and Hill, 1982, as modified by McLeod, 1985). The Participant will be assigned a number based on the order the Participant is enrolled in the study and that number will be randomly assigned to a follow-up group based on that number.

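### Section 9g, read literally, makes PROMIS Global one of three alternative forms, which conflicts with its role as the unrestricted primary endpoint and sample-size basis

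*Combined protocol and SAP*

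**What the plan says.** Four places in the combined protocol and SAP bear on who completes PROMIS Global.

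- **Section 9f (Study Endpoints)** gives the primary endpoint without any limit by joint: "Primary study endpoints: Participant reported outcome scores through PROMIS Global". The secondary instruments are tied to joints: "Patient survey scores for knee injuries via KOOS, and shoulder and elbow injuries via QuickDash".
- **Section 9g, survey list.** The list of surveys after each follow-up visit opens with "The surveys the Participant will be asked to fill out are the following". PROMIS Global is a numbered item of its own, beside KOOS, QuickDASH, two general health questionnaires and the satisfaction survey.
- **Section 9g, layout of the online survey.** The second page is "a joint specific survey and will depend on the joint selected on the first page and the language chosen". The next sentence reads "It can be the KOOS, QuickDash Outcome Measure, or PROMIS Global". The only other survey mentioned there is the satisfaction survey, described as separate.
- **Section 9i (Data Management/Statistical Analysis)** uses PROMIS Global to set the sample size: 26 per group, 52 in total, for 80% power at an effect size of 0.8 and a significance level of 0.05.

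Two further statements matter. Section 7 says that all participants complete the surveys, without naming an instrument. Section 9c sets a recruitment target of at least 104, to allow for removals and losses.

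**The concern.** The layout paragraph is the only description of how the online form branches, so anyone building or checking it in REDCap would naturally turn to it. It has a singular subject and joins the three instruments as alternatives, which puts PROMIS Global inside the branch. Combined with section 9f, knee participants would see KOOS, shoulder and elbow participants would see QuickDASH, and only the remainder would see PROMIS Global.

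If the form works that way, participants routed to KOOS or QuickDASH have no primary endpoint at 6 weeks, 12 weeks or 6 months, and a score not collected at its visit cannot be recovered at analysis. The primary comparison would cover only the remaining joints, and the 26 per group would not describe the people who have a score. The margin between 52 and 104 is meant for removals and losses, not for participants who were never shown the primary instrument.

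**Working it through.** **Step 1. The texts side by side.**

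| Place | What it implies for PROMIS Global |
|---|---|
| 9f, endpoints | Primary endpoint, no limit by joint; KOOS and QuickDASH are limited by joint |
| 9g, survey list | Own item, after each visit, no limit by joint |
| 9g, survey layout | One of three alternatives on a single joint-specific page |
| 9i, sample size | Basis for all 52 participants |
| 7, resources | All participants complete the surveys; no instrument named |

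The layout paragraph stands against the other rows. None of them says outright that PROMIS Global is given as well as the joint form.

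**Step 2. Reproduce the stated sample size.** Inputs from section 9i: effect size d = 0.8, alpha 0.05, power 80%, Student t-test. Two-sided testing and equal groups are assumed, because the hypothesis is of a difference and the stated group sizes are equal.

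For n per group, the degrees of freedom are 2n − 2 and the noncentrality is d × √(n/2). Power is the probability that the noncentral t exceeds the two-sided critical value in absolute size.

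- Solving for 80% power gives n = 25.52, rounded up to 26 per group, as stated.
- At n = 26: df = 50, critical value 2.009, noncentrality 0.8 × √13 = 2.884, power 80.7%.

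The stated figure is reproduced, and it needs a PROMIS Global score from all 52 completers.

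**Step 3. Illustrate the literal reading.** Let s be the share of participants with a PROMIS Global score. The joint mix is not in the documents, so s is an assumption, shown as a range. With N participants, n per group = s × N/2 (fractional values kept). For example, s = 50% and N = 52 gives n = 13, df = 24, noncentrality 0.8 × √6.5 = 2.040, critical value 2.064, power 49.9%.

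| Assumed share s | n per group, N = 52 | Power, 52 completers | n per group, N = 104 | Power, 104 recruits, no loss |
|---|---|---|---|---|
| 10% | 2.6 | 10% | 5.2 | 21% |
| 20% | 5.2 | 21% | 10.4 | 41% |
| 33% | 8.58 | 34% | 17.16 | 62% |
| 50% | 13 | 50% | 26 | 81% |
| 75% | 19.5 | 68% | 39 | 94% |
| 100% | 26 | 81% | 52 | 98% |

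With 52 completers, every share from 10% to 75% falls short of 80%. With all 104 recruits and no loss, a share of about half is enough (0.5 × 104/2 = 26 per group). That column is a best case, since it uses up the whole allowance for dropout.

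**The case against.** The strongest reply is that the layout paragraph is loose wording and not a routing rule. It leaves out the two general health questionnaires that the list in the same section includes, so it is not a full inventory and is weak evidence that any instrument is withheld. It calls the page joint-specific and yet names a global measure. Section 7 has all participants completing the surveys, and sections 9f and 9i attach no joint to PROMIS Global. On this view everyone receives it and only a sentence needs tidying.

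Much of this stands: loose wording is plausible. It does not remove the conflict. Section 7 names no instrument. The list in section 9g cannot be literal for every participant, because it also includes "KOOS- a knee specific survey"; if it is read as a menu, it is compatible with exclusive branching.

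A reader might infer that PROMIS Global scores will in fact be missing and that the trial has only about 50% power. The documents do not support that. The protocol says of the surveys "The mentioned above surveys will be attached to this document", but neither those attachments nor the REDCap form is available here, so the actual branching is unknown. The 50% rests on one assumed share of 52 completers; the same share of 104 recruits with no loss gives 81%. Nor does section 9i restate PROMIS Global as the primary endpoint: it uses it only to set the sample size, and the endpoint status comes from section 9f.

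**Conclusion.** The conflict in the text is real and concerns the primary endpoint. The survey layout in section 9g states a rule that, if followed as written, leaves participants routed to KOOS or QuickDASH without a PROMIS Global score, contrary to section 9f, the survey list and the basis of the sample size. It should be fixed, because the text that could be used to build the form is the text that is wrong or unclear.

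The consequence is conditional. If PROMIS Global goes to everyone, nothing is lost and only the wording changes. If the branching is exclusive, the loss depends on a joint mix that the protocol does not give and on how many of the 104 recruits complete; the table shows the span under assumed shares, a two-sided test and equal groups. None of those powers is an estimate for this trial.

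**What to change.** Rewrite the survey-layout paragraph of section 9g to state that every participant completes PROMIS Global at 6 weeks, 12 weeks and 6 months, and that KOOS (knee) or QuickDASH (shoulder and elbow) is added according to the joint selected. Align the survey list in the same section on this point, so that PROMIS Global is marked as given to all and the two joint instruments as given by joint. Then check that the REDCap branching does this, and edit it only if it is exclusive.

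The cost is a few sentences of protocol and a check of the form. The downside is at most one additional form, already on the protocol's list, for some participants.

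### PROMIS Global is the primary endpoint with no named visit, but is tested at three visits, each at 0.05; the stated 5% error fails if a difference at any visit counts

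*Combined protocol and SAP*

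**What the plan says.** Section 9f defines the primary endpoint as "Primary study endpoints: Participant reported outcome scores through PROMIS Global" and gives no time point. The research hypothesis in section 4 expects scores to differ from those of patients "who are seen during an in-person visit for post-operative follow-up at 6 weeks, 12 weeks, and 6-months", so it lists three visits on an equal footing.

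Section 9i says that "Participant outcomes scores from each appointment time frame (6-week, 12 week, and 6 months) will be compared" between the two arms by Student t-test, and that "Statistical significance will be based on an α level of 0.05". It gives no order of testing, no split of alpha and no joint model for the between-arm comparison.

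The sample size in 9c and 9i is for one comparison. Section 9i bases it on PROMIS Global with 80% power: "assuming a large effect size of 0.8, 26 Participants are required per group". Section 9c adds "The number of Participants need to complete the research procedure are 52" and, as an allowance for loss, "Locally we will attempt to recruit at least 104 Participants".

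**The concern.** There is one primary endpoint and one alpha, but there are three tests. The plan does not say whether its hypothesis is supported by a difference at one particular visit, at any visit or at all three. That choice could therefore be made after the results are seen, and a significant result at one visit of three could be reported as success or as failure.

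The choice matters because the rules behave differently. Counting any visit gives three chances of a false positive at 0.05 each. Requiring all three protects against false positives but costs power. The stated 5% and 80% describe one test, and the plan does not identify which one.

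**Working it through.** **Inputs from the documents.** Three visits (9i); alpha 0.05 (9i); power 80%, standardized effect 0.8 and 26 per arm (9c, 9i); at least 104 recruits, or 52 per arm if split equally (9c). Sidedness is not stated. Two-sided is inferred because the hypothesis is one of difference, and because it reproduces the plan's figure.

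**Inputs assumed.** The between-visit correlation r of PROMIS Global is not in the documents, so r = 0, 0.5, 0.8 and 0.9 were used, equal for all pairs of visits. Where an effect is present at every visit, it is taken as 0.8 at each.

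**1. The plan's own figure.** For a two-sided two-sample t-test, the noncentrality is 0.8 × √(n/2) with 2n − 2 degrees of freedom. Solving for 80% power at 0.05 gives n = 25.52, rounded up to 26 per arm. At n = 26 the noncentrality is 0.8 × √13 = 2.88 and power is 80.7%. A one-sided test would need only about 20 to 21. The stated 26 is therefore correct for one two-sided test.

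**2. Any visit counts, no true difference.** With independent visits the chance of at least one false positive is 1 − 0.95³ = 0.143. With correlated visits it was simulated (three t-tests, 100,000 runs).

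| r | 26 per arm | 52 per arm |
|---|---|---|
| 0 | 14.0% | 14.3% |
| 0.5 | 12.5% | 12.5% |
| 0.8 | 9.8% | 9.7% |
| 0.9 | 8.2% | 8.4% |

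Doubling the sample makes no difference beyond simulation error.

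**3. All three visits must differ.** With no true difference, error is at most about 2% (r = 0.9). Power was simulated with an effect of 0.8 at every visit. The last column is the loss from 52 per arm that still leaves enough completers, for example (52 − 38)/52 = 27%.

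| r | Power, 26 per arm | Completers per arm for 80% | Loss allowed from 52 |
|---|---|---|---|
| 0 | 53% | 38 | 27% |
| 0.5 | 62% | 35 | 33% |
| 0.8 | 70% | 32 | 38% |
| 0.9 | 73% | 31 | 40% |

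**4. One named visit.** Error is 5% and power 80.7% with 26 scores per arm at that visit, whatever the correlation. Power is 77% with 24 scores per arm, 74% with 22 and 69% with 20.

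**5. Does other text supply a rule?**
- Section 9i says "Each Participant outcomes scores will be averaged with standard deviation calculated". It does not say over what, and it names no test of an average. Group means and standard deviations are the natural reading, and the comparison that follows is made visit by visit.
- The analysis of variance in 9i concerns change in satisfaction within each group, not the between-arm comparison of PROMIS Global.
- The 104 recruits are an allowance for loss. They do not decide which test is primary.

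**The case against.** The plainest reading of 9i is three visit-specific comparisons. On that reading each conclusion has 5% error and 80.7% power with 26 per arm, and the sample size is right. Whether visit-specific conclusions need a family-wise rule is partly convention. The three tests are listed in advance, so if all are reported a reader can adjust for them. Repeated scores from one patient are likely to be correlated, so 14% is a ceiling. The background also speaks of whether virtual-visit patients report similar outcomes, and for that aim extra chances to find a difference are less harmful.

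Much of this stands. A reader might infer that error and power are wholly undetermined, or that 26 per arm is wrong. The documents do not support either, because each test taken singly has its stated properties. A reader might also infer that the trial is underpowered. The 53% to 73% applies only if all visits must differ and exactly 26 per arm complete, and the recruitment target leaves room above that.

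Nor should it be inferred that a two-of-three rule would quietly rescue the plan. No such rule is stated. With 26 per arm it would be met about 5% to 8% of the time when only one visit differs, and its power would be about 67% to 76% when exactly two differ.

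Two things survive the objection. The visit-by-visit reading still leaves no visit primary, and the chance of at least one false positive is still the any-visit figure, about 8% even at r = 0.9. The similarity argument is limited because the stated hypothesis is one of difference.

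**Conclusion.** The concern holds as a gap in the primary analysis: one primary endpoint, three tests at 0.05, a sample size for one, and no statement of which test or combination decides. The stated 5% does not hold for the primary hypothesis if any visit counts; it is then about 8% to 14%. If all visits must differ, error is controlled, but 80% power needs about 31 to 38 completers per arm instead of 26.

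These ranges rest on assumed, equal between-visit correlations of 0 to 0.9. The power figures also assume an effect of 0.8 at every visit. The absence of a named visit or rule depends on no assumption.

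This should be fixed. It does not invalidate the design or the 26 per arm.

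**What to change.** Before any outcome data are examined, name one primary visit in 9f and 9i, for example: *The primary analysis is the between-arm difference in PROMIS Global at [one visit chosen by the investigators], two-sided Student t-test at 0.05; the other two visits are secondary, reported with 95% confidence intervals.* Align the objectives and hypothesis in section 4, which would otherwise still present the three visits as equal.

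This takes a few sentences and no new data, and leaves the test, alpha and 26 per arm unchanged. The 80.7% power requires 26 PROMIS Global scores per arm at the chosen visit; from 52 recruits per arm, that allows a loss of (52 − 26)/52 = 50%. Which participants complete PROMIS Global is a separate point, to be settled on its own.

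The real cost is that two visits now listed equally in the objectives become secondary. If the investigators do not accept that, a prespecified order of testing, or an explicit statement that three separate visit-specific conclusions are intended, would also remove the ambiguity. The latter would leave the chance of at least one false positive at the any-visit level, and the plan should then say so.
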